9.5 Treatment Compliance

Study drug will be administered to subjects at the study site and/or the dosing facility by a qualified health care professional. The quantity dispensed, returned, used, lost, etc. must be recorded on a dispensing log. Sites will be instructed to return or destroy all used and unused study drug containers.

9.6 Investigational Product Accountability

The Investigator or designee is responsible for maintaining accurate records (including dates and quantities) of IP(s) received and IP lost or accidentally or deliberately destroyed. The Investigator or designee must retain all unused or expired study supplies until the study monitor (on-site CRA) has confirmed the accountability data, if allowed by local SOPs.

9.6.1 Return and Disposition of Clinical Supplies

Unused study drug must be kept in a secure location for accountability and reconciliation by the study monitor. The Investigator or designee must provide an explanation for any

Page 69

destroyed or missing study drug or study materials (or must be referenced in their institution SOPs).

Unused study drug may be destroyed on site, per the site's standard operating procedures, but only after BioMarin has granted approval for drug destruction. The monitor must account for all study drug in a formal reconciliation process prior to study drug destruction. All study drug destroyed on site must be documented. Documentation must be provided to BioMarin or designee and retained in the Investigator study files. If a site is unable to destroy study drug appropriately, the site can return unused study drug to BioMarin upon request. The return of study drug or study drug materials must be accounted for on a study drug return form provided by BioMarin.

All study drug and related materials should be stored, inventoried, reconciled, and destroyed or returned according to applicable state and federal regulations and study procedures. For additional information, please refer to the Pharmacy Manual.

9.7 Dietary or Other Protocol Restrictions

There are no dietary or other protocol restrictions for this study. Alcohol should be avoided for the first 52 weeks of the study, and particularly within 48 hours prior to lab work.

Subjects should be advised to abstain from any blood or sperm donation after BMN 270 infusion, until there is no further evidence of vector shedding from PCR analysis of samples.

9.8 Safety and Efficacy Variables

9.8.1 Safety and Efficacy Measurements Assessed

The Schedule of Events (Table 9.1.1 through Table 9.1.5) describes the timing of required evaluations.

9.8.2 Primary Efficacy Variables

9.8.2.1 FVIII Activity

The primary efficacy variable is change of the hFVIII activity, as measured by chromogenic substrate assay, during Weeks 49-52 post-BMN 270 infusion from baseline. Each subject's hFVIII activity during Weeks 49-52 is defined as the median of the values obtained during this 4-week window. Values for FVIII activity will be excluded if obtained within 72 hours since the last infusion of exogenous FVIII protein concentrates.

If a subject has used FVIII within 72 hours of a measurement day, all efforts should be made to obtain FVIII activity measurements when a 72-hour interval without FVIII use is achieved; The 72-hour wash-out period is only intended for subjects who have achieved

Page 70

FVIII \geq 5 IU/dL at 16 weeks after BMN 270 infusion and who have not resumed FVIII replacement therapy.

In the event of an FVIII activity level decline during the study:

- If FVIII activity has declined at least 20% from the peak but less than 35% and has declined for at least 2 consecutive assessments, FVIII activity and LTs should be repeated every 7 days until FVIII activity is stable or increasing
- If FVIII activity has declined >35% from the peak and has declined for at least 2 consecutive assessments, FVIII activity and LTs should be repeated every 72 hours until FVIII activity is stable or increasing

Note that fluctuations in FVIII activity are common, and if no clear trend indicating a decline in FVIII activity is observed, then this additional testing may be deferred (upon consultation between the Investigator and the Medical Monitor) until either a more clear trend of decline has been demonstrated or until the FVIII activity levels stabilize or increase.

Subjects who do not respond to BMN 270 treatment (ie treatment failure, manifesting as either failure to achieve FVIII activity ≥ 5 IU/dL by Week 52 or inability to maintain independence from prophylactic FVIII replacement therapy due to joint bleeding episodes, in the judgment of the Investigator) may, at the Investigator's discretion and after discussion with the Medical Monitor, follow an abbreviated visit schedule after Week 52 of the study by attending only the Q12W and End of Year visits during Years 2-5.

Details on collecting FVIII activity samples are included in the Laboratory Manual.

9.8.3 Secondary Efficacy Variables

9.8.3.1 Factor VIII Replacement Therapy/Bleeding Episodes

Secondary efficacy variables are:

- Change of the annualized utilization (IU/kg) of exogenous FVIII replacement therapy during Week 5 to Week 52 post BMN 270 infusion from the baseline utilization of exogenous FVIII replacement therapy.
- Change in the annualized number of bleeding episodes requiring exogenous FVIII replacement treatment during Week 5 to Week 52 of the study post BMN 270 infusion from the baseline ABR.

Subjects must have high quality documented historical data available concerning previous bleeding episodes and exogenous FVIII usage over the previous 12 months in order to be eligible to enroll in the study. During the study, subjects will be asked at each study visit to report the use of factor replacement therapy and the number of bleeding episodes since the

Page 71

previous visit. This information will be captured on the subject's diary or other subject records.

Subjects are strongly encouraged to immediately consult Investigator for guidance regarding exogenous FVIII administration for suspected bleeds or bleeding episodes within the first 30 days post BMN 270 infusion.

In subjects who experience recurrent bleeding episodes, the Investigator and Medical Monitor will discuss whether to resume prior FVIII prophylaxis.

9.8.4 Tertiary Efficacy Variables

9.8.4.1 Patient-Reported Outcomes (PRO)

The Haemo-QoL-A questionnaire is a validated hemophilia-specific health-related quality of life questionnaire for adults (Rentz, 2008). It consists of 41 questions covering six domains (Physical Functioning, Role Functioning, Worry, Consequences of Bleeding, Emotional Impact and Treatment Concerns). Items are answered on a 6-point Likert-type scale, ranging from 0 (None of the time) to 5 (All of the time). Higher scores mean better health-related quality of life or less impairment for a particular subscale (Haemo-QoL Study Group, 2017). Details regarding the Haemo-QoL-A assessment will be included in the On Site File Binder.

The EQ-5D-5L instrument is a self-reported questionnaire designed to measure general health status (The EuroQol Group, 1990) (Brooks, 1996). The EQ-5D-5L is composed of 2-parts: a descriptive system that assesses 5 levels of perceived problems (mobility, self-care, usual activities, pain/discomfort, and anxiety/depression) in 5 dimensions and the EQ visual analogue scale (EQ VAS) assessment for overall health. A sample copy of the EQ-5D-5L and additional information are provided in the On Site File Binder.

The Haemophilia Activities List (HAL) measures the impact of hemophilia on self-perceived functional abilities in adults (Van Genderen, 2006). The instrument consists of multiple domains including lying/sitting/kneeling/standing, leg and arm function, use of transportation, self-care, household tasks, and leisure activities where subjects are asked to rate their level of difficulty with activities of daily living on a 6-point Likert-type scale from 1 (Impossible) to 6 (Never). For some items, subjects are given the choice to answer 'Not applicable'. A sample copy of the HAL and additional information are provided in the On Site File Binder.

The Work Productivity and Activity Impairment plus Classroom Impairment Questions: Hemophilia Specific (WPAI+CIQ:HS) instrument is designed to measure the effect of disease symptom severity on work productivity and classroom productivity (if applicable)

Page 72

(Recht, 2014). The WPAI+CIQ:HS questionnaire yields scores related to work/classroom absenteeism, reduced on-the-job effectiveness, overall work/classroom impairment, and activity impairment. WPAI+CIQ:HS outcomes are expressed as impairment percentages, with higher numbers indicating greater impairment and less productivity (Reilly, 2002). A sample copy of the WPAI+CIQ:HS and additional information are provided in the On Site File Binder.

The Patient Reported Outcomes, Burdens, and Experiences (PROBE) questionnaire is designed to investigate and directly probe patient perspectives on outcomes they deem relevant to their life and care. PROBE aims to develop a new global tool to enhance the direct patient-voice in health care decision-making (Chai-Adisaksopha, 2017). A sample copy of the PROBE questionnaire and additional information are provided in the On Site File Binder.

9.8.5 Immunogenicity

Immunogenicity assays will be performed on plasma and PBMCs. The assays will include detection of anti-AAV5 capsid and anti-FVIII total antibodies, as well as determination of neutralizing antibodies against FVIII (FVIII inhibitors) and against the AAV5 capsid (Transduction Inhibitors, TI). FVIII Inhibitors will be assessed using the Bethesda assay with Nijmegen modification. Any abnormality of the liver parameters will lead to a retrospective immunogenicity assessment to evaluate FVIII- and capsid-specific cellular immunogenicity. FVIII- and capsid-specific cellular immunity will be assessed by stimulated cytokine secretion using an ELISpot assay performed on collected PBMCs.

9.8.6 Pharmacodynamics

The FVIII protein concentration and activity level as measured by a validated immunoassay and by a validated FVIII activity assay, respectively, will be used for plasma profiles; FVIII protein and activity will be used to determine PD parameters.

9.8.7 Exploratory Assessments

Blood samples will be collected from subjects at the time points indicated in Table 9.1.1, Table 9.1.2, Table 9.1.3, Table 9.1.4, and Table 9.1.5 to evaluate biochemical, molecular, cellular, ABO blood typing, and genetic/genomic aspects relevant to hemophilia A, coagulation, and/or AAV gene transfer, and to develop assays used for these evaluations. Subjects may choose to opt out of the exploratory genetic/genomic research being done to study or try to discover genes that are not yet known to be associated with hemophilia A.

Page 73

All biomarker samples collected in this study may be used for exploratory biomarker research, including evaluation of additional biomarkers not specifically listed in the protocol. In addition, samples collected for other purposes in this study may be used for exploratory research once testing for the primary purpose has been completed.

9.8.8 Safety Variables

Safety in this study will be determined from evaluation of AEs, clinical laboratory assessments with a particular attention to the liver function, vital signs assessments, physical examinations, and immunogenicity.

9.8.8.1 Adverse Events

The determination, evaluation and reporting of AEs will be performed as outlined in Section 10.

9.8.8.2 Clinical Laboratory Assessments

The scheduled clinical laboratory tests are listed in Table 9.8.8.2.1. Refer to the On Site File Binder for instructions on obtaining and shipping samples.

Any abnormal test results determined to be clinically significant by the Investigator should be repeated (at the Investigator's discretion) until: (1) the cause of the abnormality is determined; (2) the value returns to baseline or to within normal limits; or (3) the Investigator determines that the abnormal value is no longer clinically significant.

All abnormal clinical laboratory results should be initialed and dated by an Investigator, along with a comment regarding whether or not the result is clinically significant. Each clinically significant laboratory result should be recorded as an adverse event.

The diagnosis, if known, associated with abnormalities in clinical laboratory tests that are considered clinically significant by the Investigator will be recorded on the AE eCRF.

Page 74

Table 9.8.8.2.1: Clinical Laboratory Tests

Blood Chemistry	Hematology	Urine Tests	Coagulation Screen including:
Albumin	Hemoglobin	Appearance	APTT
BUN	Hematocrit	Color	PT/INR
Calcium	WBC count	рН	TT
Chloride	RBC count	Specific gravity	
Total cholesterol	Platelet count	Ketones	
CPK	Differential cell count	Protein	
Creatinine	RBC indices (MCV and MCH)	Glucose	
CRP		Bilirubin	
Glucose		Nitrite	
Phosphorus		Urobilinogen	
Potassium		Hemoglobin	
Total protein			
Sodium			
Uric Acid			

BUN, blood urea nitrogen; CPK, creatinine phosphokinase; CRP, C-reactive protein; PT, prothrombin time; APTT, activated partial thromboplastin time; RBC, red blood cell; WBC, white blood cell; TT, thrombin time; INR, international normalized ratio; MCV, mean corpuscular volume; MCH, mean corpuscular hemoglobin.

In addition to scheduled clinical laboratory assessments, a fasting blood lipid panel (including triglycerides, total cholesterol, HDL cholesterol, and LDL cholesterol) will be assessed at the BMN 270 infusion visit. Subjects will fast for at least 8 hours prior to pre-infusion laboratory sampling on the day of the infusion visit.

In case of hypersensitivity or adverse drug reaction, safety assessment, including physical examination and vital signs, will be done and additional blood samples will be collected within 1 hour of the hypersensitivity reaction (eg, tryptase, C3, C3a, C4, C5, C5a, and cytokine bead array, as well as possible additional exploratory testing) and samples for IgE and cytokine bead array (and possible additional exploratory testing) between 8-24 hours after the reaction. In addition, a blood sample should be taken 1 week after the hypersensitivity reaction for assessment of the cytokine bead array.

During Years 2-5, at applicable sites, certain study assessments may be performed by a mobile nursing (MN) professional at the patient's home or another suitable location, such as their school or office, to improve access and convenience for patients participating in the

Page 75

MN services for participating sites (the MN vendor). The MN vendor is responsible for ensuring that all MN professionals are licensed, qualified, and in good standing, as per applicable regulations, and that appropriate background checks have been performed. If the investigator at a participating site determines that MN services are appropriate for a patient and the patient gives written informed consent to participate in MN visits, the MN network will communicate with the patient and the patient's site. MN visits will be allowed for the Q4W (during Year 2) and Q6W (during Years 3-5) visits; the Q12W visits and End of Year visits during Years 2-5 will not be performed by an MN professional but will be done at the study site.

9.8.8.3 Liver and Hepatitis Testing

Subjects will be screened for evidence of previous or active hepatitis B or hepatitis C infection at Screening; hepatitis B screening should include HBsAg, HBsAb, and HBcAb. Subjects with documented results showing an absence of active hepatitis B or hepatitis C infection (as measured by positive surface antigen for hepatitis B or positive RNA testing for hepatitis C) 30 days prior to providing signed informed consent do not need to repeat those tests during the screening period.

Evidence of ongoing hepatitis B or hepatitis C infection is exclusionary. Subjects with a history of hepatitis B or hepatitis C infection prior to study entry will be tested for hepatitis B and hepatitis C reactivation at Week 16. Subjects with a history of hepatitis B or hepatitis C will be asked for information about the treatments received as part of their medical history assessment at Screening.

Subjects with a previous history of hepatitis B or hepatitis C who receive therapeutic oral corticosteroids prior to Week 16 do not need to complete the Week 16 reactivation assessment; instead, they will be tested for hepatitis B and hepatitis C reactivation at the time points listed in Table 9.1.6.

A liver ultrasound and liver tests (LTs) during Screening will identify any significant hepatic dysfunction.

LTs will be monitored on a regular basis; at each time point, the following LTs should be assessed:

Page 76

Table 9.8.8.3.1: Liver Tests

Liver Tests (LTs)				
Alkaline Phosphatase	AST (SGOT)	Total Bilirubin	LDH	
ALT (SGPT)	Direct Bilirubin	GGT		

ALT, alanine aminotransferase; AST, aspartate aminotransferase; GGT, gamma-glutamyltransferase; LDH, lactate dehydrogenase; SGOT, serum glutamic-oxaloacetic transaminase; SGPT, serum glutamic-pyruvic transaminase

Elevated ALT levels (above the upper limit of normal range) should be evaluated according to the following plan:

Page 77

Table 9.8.8.3.2: Evaluation of ALT Elevations

ALT Level	Work-Up
Above ULN and <1.5x ULN	• Continue to monitor LTs and FVIII per protocol (repeat within 7 days if next protocol scheduled visit is >7 days from the time of the reported ALT elevation)
	 Consider evaluation to rule out alternative etiology (eg, concomitant medications, viral or autoimmune hepatitis, alcohol use, recreational drug use, special diets, strenuous exercise, prior and/or concurrent illnesses, exposure to environmental and/or industrial chemicals, etc.) (refer to Table 9.8.8.3.3)
	• If ALT is > ULN & > 2x baseline in 2 consecutive assessments within 72 hours and alternative etiologies have been ruled out, start oral corticosteroids upon consultation with the Medical Monitor (refer to Section 9.4.8.2)
1.5 - <3x	Repeat LTs and FVIII within 72 hours
ULN	 Continue to monitor LTs weekly until ALT is stable or improving
	 Evaluate and rule out alternative etiologies (as above)
	Consult with Medical Monitor
	• If ALT is ≥ 1.5x ULN in 2 consecutive assessments within 72 hours and alternative etiologies have been ruled out, start oral corticosteroids (refer to Section 9.4.8.2)
≥3x ULN	Consult with Medical Monitor
	 Evaluate and rule out alternative etiologies (as above)
	• Repeat LTs and FVIII within 48 hours, and continue with monitoring of LTs at least twice weekly for as long as the subject's ALT remains $\geq 3x$ ULN
	• If ≥ 3x ULN in 2 consecutive assessments within 48 hours, start oral corticosteroids (refer to Section 9.4.8.2)
	 Obtain other possibly relevant laboratory evaluations (albumin, PT/INR, CRP, etc.)
	 Obtain complete blood count with differential to assess for eosinophilia
	 Obtain PBMC to evaluate potential immune response (prior to starting oral corticosteroids)
	• If no improvement in 14 days, consider gastroenterology and/or hepatology consult, abdominal workup, imaging (including MRI or ultrasound), and/or liver biopsy as appropriate

Page 78

When ruling out alternative viral or autoimmune hepatitis as part of the elevated ALT workup, the following tests should be performed:

Table 9.8.8.3.3: Viral and Autoimmune Hepatitis Testing

Viral Hepatitis Workup Testing	Autoimmune Hepatitis Workup Testing	
Hepatitis A	Smooth muscle antibody	
Hepatitis B	Mitochondrial antibody	
Hepatitis C	Liver/kidney microsomal antibodies	
Hepatitis E	Antinuclear antibody (ANA) HEP-2	
Cytomegalovirus (CMV)		
Epstein-Barr virus (EBV)		
Herpes simplex virus (HSV) 1 & 2		

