To avoid breakthrough bleeding, subjects will only discontinue exogenous prophylactic FVIII replacement therapy after 4 weeks following infusion of BMN 270. Four weeks represents the time by which endogenous production of FVIII following gene transfer is expected to be efficacious, based on earlier results.

As the relationship between activity assay results of the BMN 270 gene product and bleeding remains to be established, Investigators should strive to minimize bias by avoiding consideration of FVIII activity levels by themselves or subjects in the reporting of bleeding episodes and FVIII usage.

In subjects who experience recurrent bleeding episodes, the Investigator and Medical Monitor will discuss whether to resume prior FVIII prophylaxis.

Subjects who do not respond to BMN 270 treatment (ie, treatment failure, manifesting as either failure to achieve FVIII activity ≥ 5 IU/dL by Week 52 or inability to maintain independence from prophylactic FVIII replacement therapy due to joint bleeding episodes, in the judgment of the Investigator) may, at the Investigator's discretion and after discussion with the Medical Monitor, follow an abbreviated visit schedule after Week 52 of the study by attending only the Q12W and End of Year visits during Years 2-5.

There will be an ongoing review of individual subject safety by the Medical Monitor, and both safety and efficacy data by the DMC. Therapeutic oral corticosteroids may be initiated when a subject's ALT values are elevated, and subsequent dosage adjustments made, after consultation between the Investigator and the Medical Monitor. Management of ALT elevations is discussed in more detail in Section 9.8.8.3.

Any safety signal may trigger a review of the data and possible additional immunogenicity studies or other diagnostics deemed necessary that include an assessment of cellular immune responses using collected peripheral blood mononuclear cells (PBMCs).

Page 41

Schedules of assessments for the Screening and Infusion period (Table 9.1.1), Post-Infusion follow-up periods (Table 9.1.2, Table 9.1.3, Table 9.1.4, Table 9.1.5), and during the use of oral corticosteroids (Table 9.1.6) are presented below.

Table 9.1.1: Schedule of Events – Screening and Infusion

	Pric	or to BMN 270 Infusion		BMN 270
Assessment	Screening* (Day -28 to Day -1)	Smart Rescreening ⁱ (Day -28 to Day -1)	Baseline (Day -7 to Day -1)h	Infusion Visit (Day 1)k
Informed consent	X			
Demographics (age, sex, race, ethnicity)	X			

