9.4.8.2 Therapeutic Glucocorticoid Treatment of Elevated Hepatic Transaminases

Therapeutic oral corticosteroids (prednisone or converted equivalent) should be initiated when either of the following occurs post-BMN 270 infusion in any subject and after consultation with the Medical Monitor (or their designee):

- ALT \geq 1.5x ULN or ALT > ULN & > 2x baseline value in 2 consecutive assessments within 72 hours and alternative etiologies have been ruled out, or ALT \geq 3x ULN in 2 consecutive assessments within 48 hours (refer to Table 9.8.8.3.2)
 - Whenever possible, a confirmatory lab draw for ALT should be performed, along with FVIII activity, prior to initiating oral corticosteroids.
 - Corticosteroids may be delayed if elevations in ALT are clearly not related to BMN 270 (eg, elevated ALT with concurrent increase in CPK due to intensive exercise)

The prescribed regimen for therapeutic oral corticosteroids is detailed in Table 9.1.6. Changes to the corticosteroid regimen should be made as follows:

Table 9.4.8.2.1: Adjustments to Corticosteroid Regimen

Tapering Corticosteroid Dose	Subject has been receiving oral corticosteroids <3 weeks Subject has been receiving oral corticosteroids ≥3 weeks	 Corticosteroids may be discontinued if: ALT < 1.5x ULN or ALT ≤ ULN & ≤2x baseline value; and FVIII levels > 20 IU/dL and within 10% of the pre-decline FVIII levels; and There is no concern for adrenal insufficiency post-withdrawal Corticosteroids may be tapered by 10 mg weekly if: ALT < 1.5x ULN or ALT ≤ ULN & ≤2x baseline value; and FVIII levels > 20 IU/dL and within 10% of the pre-decline FVIII levels; and There is no concern for adrenal insufficiency post-withdrawal
Increasing Corticosteroid Dose		reasing or FVIII level is decreasing while on oral corticosteroids, any rticosteroid dosing should be made only upon consultation with the

For any scenarios that are not accounted for in the above table, a discussion should take place between the Investigator and Medical Monitor regarding corticosteroid dose adjustments.

After discontinuation of oral corticosteroids, labs for ALT and FVIII levels will be measured once a week for 4 weeks to ensure stability in values.

Following initiation or completion of therapeutic oral corticosteroids, if ALT elevation $\geq 1.5 \text{x}$ ULN or ALT \geq ULN & $\geq 2 \text{x}$ baseline value is reported, corticosteroid management decisions will be based on discussions between the Investigator and Medical Monitor.

Page 68

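### The lowest ALT row's steroid trigger needs two tests within 72 hours, but the row orders a repeat only at the next visit or within 7 days

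*Protocol*

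**What the plan says.** The current (Amendment 3) text of Table 9.8.8.3.2 has three ALT rows.

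The lowest row, above ULN and under 1.5x ULN, sets the testing rule "Continue to monitor LTs and FVIII per protocol (repeat within 7 days if next protocol scheduled visit is >7 days", with the 7 days counted from the reported elevation. On cause it says "Consider evaluation to rule out alternative etiology". It then gives a steroid trigger: "If ALT is > ULN & > 2x baseline in 2 consecutive assessments within 72 hours and alternative etiologies have been ruled out", with the start made in consultation with the Medical Monitor. Section 9.4.8.2 states the same condition: "ALT > ULN & > 2x baseline value in 2 consecutive assessments within 72 hours and alternative etiologies have been ruled out".

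The middle row (1.5 to under 3x ULN) orders "Repeat LTs and FVIII within 72 hours". The top row (3x ULN or more) orders "Repeat LTs and FVIII within 48 hours, and continue with monitoring of LTs at least twice weekly". Both also require other causes to be evaluated and ruled out.

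**The concern.** In the middle and top rows, a site that does what the row says collects the data needed to decide whether the steroid trigger is met. In the lowest row it does not. The second ALT may come a week after the first, while the trigger counts only two successive tests no more than 72 hours apart. The trigger also needs other causes excluded, but the row does not require anyone to look for them.

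At stake is whether sites start steroids consistently for mild but persistent ALT rises. Section 7.4 reports that in study 270-201 most elevations were only slightly above ULN, and that steroids were given to preserve the transduced liver cells. The mismatch therefore sits in the range where rises are expected. Amendment 2 had the same 7-day repeat with no steroid trigger in this row. Amendment 3 added the trigger and left the repeat interval as it was.

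**Working it through.** The plan gives no figure to reproduce. The check compares what each row orders with what its trigger needs, then looks for any rule elsewhere that closes the gap.

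**1. Rows side by side (Table 9.8.8.3.2)**

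| ALT row | Repeat ordered | Trigger window | Other causes |
|---|---|---|---|
| Above ULN, <1.5x ULN | Next visit, or within 7 days of the report if that visit is more than 7 days away | 72 h | Optional |
| 1.5 to <3x ULN | 72 h | 72 h | Required |
| ≥3x ULN | 48 h | 48 h | Required |

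**2. Can scheduled visits supply the second test?** From Day 8 to Week 36 visits are weekly, ±48 hours (Sections 12.5 and 12.6). The gap between consecutive visits is 7 ± (2 + 2) days, so 3 to 11 days, or 72 to 264 hours; nominally it is 168 hours. Two visits fall within 72 hours only if the first is as late and the second as early as allowed. In Weeks 37 to 52 visits are nominally 14 days (336 hours) apart, ±1 week each, and the 7-day repeat is the usual backstop.

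**3. Size of the mismatch.** If both clocks are assumed to start at the first draw, 7 × 24 = 168 hours and 168 − 72 = 96 hours. On the same assumption the other rows give 72 − 72 = 0 and 48 − 48 = 0. The protocol does not state that assumption. The 7 days run from the report of the elevation, whereas the trigger's 72 hours are the spacing between tests. With an unstated reporting lag L, the latest permitted draw-to-draw gap under the 7-day repeat is 168 + L hours. The other rows do not say when their 72 or 48 hours begin.

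**4. Who can fall in the gap?** The trigger adds something below 1.5x ULN only if 2 × baseline < 1.5 × ULN, that is, baseline < 0.75x ULN.
- Baseline ≤0.5x ULN: 2 × 0.5 = 1.0x ULN, so every value in the row qualifies.
- Baseline 0.6x ULN: 2 × 0.6 = 1.2x ULN, so values above 1.2x and below 1.5x ULN qualify.
- Baseline 0.75x ULN: 2 × 0.75 = 1.5x ULN, so none do.

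The protocol gives no baseline ALT distribution, so no head count follows.

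**5. Does another rule require a 72-hour repeat?**
- Schedule footnotes (Tables 9.1.2 to 9.1.5) and Sections 12.5.1 and 12.7.1 to 12.7.3: LT frequency may be changed after discussion, and this ALT band is named for that. Permitted, not required.
- The same footnotes: extra testing once ALT exceeds ULN. Permitted.
- Section 9.4.8.2: a confirmatory draw before steroids where possible, with no time limit.
- Section 10.2.1: this band is reportable within 24 hours of site awareness. A report, not a retest.
- Twice-weekly LTs: mandatory only at 3x ULN or more.
- Section 9.8.2.1: "FVIII activity and LTs should be repeated every 72 hours", but only after FVIII has fallen more than 35% from peak over at least two consecutive assessments, and deferrable if there is no clear trend.

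None makes a 72-hour repeat mandatory for an isolated ALT rise in this band.

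**The case against.** The best defence is that discretion was intended. The Amendment 3 rationale (item 10) describes the added criterion as giving flexibility for a timely start after Medical Monitor consultation, and among the table's start instructions only this row's repeats that consultation. The protocol also singles out this ALT band, alongside 1.5x ULN and above, for adjusted monitoring. A careful reader of the trigger can see that a 72-hour repeat is needed, and the 24-hour report brings the sponsor in early. Optional work-up is sensible for a row that also covers ALT not above twice baseline.

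Much of this stands, and it limits the consequence. It does not remove the mismatch. Flexibility about starting treatment is different from a stated criterion whose evidence the same row does not ask for, and the middle row, with the same 72-hour trigger, does order the repeat.

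Two stronger readings are tempting. One is that a missed trigger leaves the subject untreated. The text does not say that: Section 9.1 provides that "Therapeutic oral corticosteroids may be initiated when a subject's ALT values are elevated", after consultation, and Section 9.4.8.2 says when steroids should start without forbidding them otherwise. If the repeat reaches 1.5x ULN, the middle row's mandatory repeat and work-up take over. The other is that the lowest row runs exactly 96 hours late and the others exactly on time. That holds only if every clock starts at the first draw.

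**Conclusion.** The point holds as an internal mismatch in one row of Table 9.8.8.3.2. A compliant site would normally retest at about 7 days, and those two tests could not document a 72-hour trigger even if ALT stayed high. The gap is confined to isolated rises that stay below 1.5x ULN in subjects whose baseline ALT is below 0.75x ULN. For them, whether and when steroids start depends on the investigator and Medical Monitor rather than on the stated criterion, so practice may differ between sites.

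Confidence in the mismatch is high. Its clinical size is unknown: neither the number of subjects nor the effect on Weeks 49-52 FVIII activity can be derived. A reader might infer harm to the primary endpoint, but the protocol gives no figures to support that. The correction is cheap and concerns a safety instruction, so it should be made.

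**What to change.** Split the lowest row of Table 9.8.8.3.2 at the next amendment.

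- ALT above ULN and more than twice baseline: repeat LTs and FVIII within 72 hours of the first draw, evaluate and rule out other causes, and consult the Medical Monitor. The steroid trigger stays as written.
- ALT above ULN but not more than twice baseline: keep the present 7-day repeat and optional work-up, reworded to apply to this group only. Without that rewording, two repeat intervals would apply to the same ALT value.

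The trigger in Section 9.4.8.2 can stay unchanged. The cost is one earlier LT and FVIII draw and an etiology work-up for each qualifying rise, which the protocol already requires at 1.5 to under 3x ULN.
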